### 5.3.1 Specimen Labeling

[figure not shown]
### 5.3.1.1 Blood and Bone Marrow Aspirate Specimen Labels

Include the following on blood specimens (including whole blood and frozen, processed blood products – like serum and plasma) and bone marrow specimens:

- Patient Study ID
- Universal Patient ID (UPID)
- Specimen ID (automatically generated by Rave)
- Time point
- Specimen type (*e.g.*, blood, serum)
- Collection date and time (to be added by hand)

### 5.3.1.2 Example of Specimen Label

The following image is an example of a tissue specimen label printed on a standard Avery label that is 1” high and 2.625” wide.

The QR code in the above example is for the Specimen ID shown on the second line.

**NOTE:** The QR code label is currently under development at Theradex as of 31-Aug-2018; therefore, labels generated by the STS for this study may not include a QR code.

The second line item from the end includes four data points joined together:

1. Tissue only: Primary (P), Metastatic (M), Normal (N) tissue indicated at the beginning of the specimen ID; this field is blank if not relevant (*e.g.*, for blood)
2. Block ID or blank if not relevant
3. SPID (Surgical Pathology ID) or blank if none
4. The last alpha-numeric code is protocol specific and is only included if the protocol requires an additional special code classification

The last line on the example label is for the handwritten date and optional time.

### 5.3.2 Overview of Process at Treating Site

#### 5.3.2.1 OPEN Registration

All registrations will be performed using the OPEN system. OPEN communicates automatically with the IWRS which handles identifier assignments, any study

randomization and any prescribed slot assignments. If specimen analysis is required to determine eligibility, the protocol will be setup with multi-step registration.

Registration without eligibility specimen analysis:

1. Site enters registration data into OPEN during one or more steps.
2. IWRS receives data from OPEN, generates the Patient Study ID and the Universal Patient ID, both of which are sent back to OPEN.
3. IWRS sends all applicable registration data directly to Rave at the end of the final registration step.

Any data entry errors made during enrollment should be corrected in Rave.

### 5.3.2.2 Rave Specimen Tracking Process Steps

**Step 1:** Complete the **Histology and Disease** form (but do not upload reports until a specimen label can be applied to them) and the Baseline forms regarding **Prior Therapies**. Enter the initial clinical specimen data:

- **Specimen Tracking Enrollment** CRF: Enter Time Point, Specimen Category, Specimen Type, Block number (if applicable), Tissue type, Surgical Path ID, number of labels needed (include extra labels to apply to reports to be uploaded). CRF generates unique Specimen ID.

**Step 2:** Print labels using report in EDC and collect specimen.

- Label specimen containers and write collection date and time on each label.
- After collection, store labeled specimens as described in Section 5.4.
- Apply an extra specimen label to *each* report before scanning. Return to the **Histology and Disease** form to upload any initial Pathology, Bone Marrow, and/or Molecular Reports (up to 4), Surgical reports and Pathology Verification form (when applicable). Return to **Specimen Tracking Enrollment** CRF to upload any molecular report (one per specimen) and/or specimen specific pathology or related report (one per specimen). Uploaded reports should have protected health information (PHI) data, like name, mailing address, medical record number or social security number (SSN) redacted. Do not redact the surgical pathology ID (SPID), block number or relevant dates (such as collection date), and include the UPID and patient ID on each document.

**Step 3:** Complete specimen data entry.

- **Specimen Transmittal** Form: Enter Collection date and time and other required specimen details.

**Step 4:** When ready to ship, enter shipment information.

- **Shipping Status** CRF: Enter tracking number, your contact information, recipient, number of containers and ship date once for the 1st specimen in a shipment.
- **Copy Shipping** CRF: Select additional specimens to add to an existing shipment

referenced by the tracking number.

**Step 5:** Print shipping list report and prepare to ship.

- Print two copies of the shipping list, one to provide in the box, the other for your own records.
- Print pathology or other required reports to include in the box. Be sure the printed copy includes the specimen label.

**Step 6:** Send email notification.

- For only one of the specimens in the shipment, click “Send Email Alert” checkbox on the **Shipping Status** CRF to email recipient.

**Step 7:** Ship the specimen(s).

## 5.4 Specimen Collection

### 5.4.1 Collection of Blood in EDTA Tubes for Plasma Processing (shipped to Karmanos Cancer Institute)

1. Label EDTA tubes according to the instructions in Section 5.3.1.
2. Collect 25 mL blood in EDTA tube(s) and gently invert tube to mix.
3. Within 1 h after blood collection, plasma will be separated from the blood sample by centrifugation (1500 x g, 10 minutes, at 4°C)
4. Using a clean transfer pipette, disperse plasma into labeled vials (using the label printed from the ETCTN Specimen Tracking System or following the instructions in Section 5.3.1) creating 4 aliquots of approximately equal volume. Avoid picking up the blood cells when aliquoting by keeping the pipet above the cell layers and leaving a small amount of plasma in the tube.
5. Tightly secure the cap of the vials before storage. Aliquoting and freezing of plasma specimens should be completed within 1 hour of centrifugation.

Store plasma vials upright in a specimen box or rack in a -80°C freezer prior to shipping to the Karmanos Cancer Institute. Do not allow specimens to thaw after freezing.

### 5.4.2 Collection of Bone Marrow Aspirate for Frozen Samples (shipped to Karmanos Cancer Institute)

1. Label EDTA tubes according to the instructions in Section 5.3.1.
2. Collect 2-3 mL bone marrow aspirate in each EDTA tube and gently invert tube to mix. Bone marrow aspirates will be processed within 1 hour of collection: bone marrow will be layered on Ficoll without dilution, spun at 450g for 20 min with breaks off, and 4 aliquots will be made and frozen in chilled FBS 90%/DMSO 10% at -80°C prior to delivering to laboratory. Do not allow specimens to thaw after freezing.
3. Bone marrow collections for each assay should be collected in separate tubes, with slight adjustment of the aspirate needle for each pull (and visual confirmation of spicules to confirm quality of aspirate).

### 5.4.3 Collection of Peripheral Blood or Bone Marrow Aspirate for Fresh Samples (shipped to

the EET Biobank or Yale University)

1. Label EDTA tubes according to the instructions in Section 5.3.1.
2. Collect peripheral blood or bone marrow aspirate in each EDTA tube (refer to Section 5.1 for volumes), and gently invert to mix.
3. Samples may be sent in the EDTA tubes at ambient temperature if received within 24 hours (must ship same day).
4. Ship on day of collection (whenever possible) according to instructions in section 5.6.
5. If bone marrow cannot be shipped on the day of collection, they need to be ficolled and viably cryopreserved within 24 hours of procedure (FBS 90%/ DMSO 10% or other freezing medium) on site and shipped at a later time on dry ice.

## **5.5 Shipping Specimens from the Clinical Site to the EET Biobank**

### **5.5.1 Specimen Shipping Instructions**

#### **5.5.1.1 Shipping Fresh Blood or Bone Marrow**

The following supplies are needed to ship whole blood or bone marrow: (1) a sturdy shipping container (e.g., a cardboard or styrofoam box), (2) a leak proof biohazard envelope with absorbent material\*, (3) a puncture and pressure resistant envelope (e.g. Tyvek envelope), (4) an Exempt Human Specimen sticker, and (5) a pre-paid FedEx air bill.

1. Before packaging specimens, verify that each specimen is labeled according to the instructions above and that lids of all primary receptacles containing liquid are tightly sealed.
2. Place the specimens in zip-lock bags. Use a separate zip-lock bag for each specimen type and time point.
3. Place the zip-lock bags in the biohazard envelope containing absorbent material. Expel as much air as possible and seal securely.
4. Wrap the biohazard envelope with bubble wrap or other padded material.
5. Put the padded specimens into a Tyvek envelope. Expel as much air as possible and seal securely.
6. Place the Tyvek envelop in a sturdy shipping container (e.g., cardboard FedEx box).
7. Insert a copy of the required forms into a plastic bag and place in the box.
8. Close the outer lid of the shipping box and tape it shut with durable sealing tape.
9. Complete a FedEx air bill and attach to top of shipping container.
10. Attach an Exempt Human Specimen sticker to the side of the shipping container.
11. Ship specimens via overnight courier to the address below. FedEx Priority Overnight is strongly recommended to prevent delays in package receipt.

## 5.6 Shipping Specimens from the Clinical Site to Other Laboratories

### 5.6.1 Shipping of Specimens to Karmanos Cancer Institute

#### 5.6.1.1 Specimen Shipping Instructions

All frozen plasma, blood, and tumor samples should be placed in cardboard tray/box, so samples remain upright. This tray/box is to be placed in a Styrofoam carton with 10-15lbs of dry ice (block with or without pellets) to keep samples frozen during shipping. A copy of PK sheets should be in the shipping box, reflecting the samples that are being sent. Samples should be shipped via FedEx Priority Overnight service. Please notify [name] via email ([[contact]](mailto:[contact])) when samples are shipped and include the shipment tracking number.

Samples can be batched and shipped.

### 5.7 Biomarker Plan

#### List of Biomarker Assays in Order of Priority

Priority	Biomarker Name	Biomarker Assay	Biomarker Type and Purpose	M/O	Specimen(s) and Time Point(s)	Laboratory Performing Assay
1	IDH1/2 Mutation	DNA sequencing or PCR	
 
Integral
 
Eligibility criteria
 
	M	
 
Bone marrow aspirate
 
Enrollment
 
	Local CLIA-certified laboratory
2	2HG Levels	LC-MS/MS	
 
Integrated
 
Potential biomarker of response
 
	M	
 
Plasma
 
Enrollment, after Cycles 1, 3, 6, 9, 12, and end of treatment
 
	[name], Karmanos Cancer Institute [contact]
3	2HG Levels	LC-MS/MS	
 
Exploratory
 
Potential biomarker of response
 
	M/O	
 
Bone marrow aspirate
 
Mandatory: enrollment
 
Optional: after Cycles 1, 3, 6, 9, 12, and end of treatment
 
	[name], Karmanos Cancer Institute [contact]
4	Genomic Profiling	Whole exome sequencing	
 
Exploratory
 
To evaluate clonal evolution and clonal architecture
 
	M/O	
 
DNA from buccal swab (enrollment only)
 
DNA from bone marrow aspirate*
 
DNA from blood
 
Mandatory: enrollment, after Cycles 1, 3, 6, 9, and 12
 
Optional: end of treatment
 
End of Cycle 1: IDHi-naïve cohorts only
 
	[name] – MoCha, National Cancer Institute [contact]
5	Genomic Profiling	RNA sequencing	
 
Exploratory
 
To evaluate clonal evolution and clonal architecture
 
	M/O	
(Will be assessed using RNA from bone marrow aspirate and blood obtained from WES biomarker.)
 
 
Mandatory: enrollment, after Cycles 1, 3, 6, 9, and 12
 
Optional: end of treatment
 
End of Cycle 1: IDHi-naïve cohorts only
 
	[name] – MoCha, National Cancer Institute [contact]
6	Genomic Profiling	Single Cell DNA Sequencing	
 
Exploratory
 
Evaluation of the clonal heterogeneity/evolution by single cell DNA sequencing
 
	M/O	
Samples from the biorepository will be used
 
 
bone marrow sample at enrollment, after Cycles 1 (optional), 3, 6, 12 and end of treatment
 
	[name], Yale University [contact] [name], Yale University [contact]
7	Avatar Studies	PDX model	
 
Exploratory
 
To evaluate disease response
 
	M	
 
Bone marrow aspirate
 
Enrollment
 
	[name], Yale University [contact] [name], Yale University [contact]

Priority	Biomarker Name	Biomarker Assay	Biomarker Type and Purpose	M/O	Specimen(s) and Time Point(s)	Laboratory Performing Assay
8	Genomic Profiling	Infinium methylation array	
 
• Exploratory
 
• To evaluate clonal evolution and clonal architecture
 
	M/O	(Will be assessed using DNA from bone marrow aspirate and blood obtained from WES biomarker.) 
 
• Mandatory: enrollment, after Cycles 1, 3, 6, 9, and 12
 
• Optional: end of treatment
 
• End of Cycle 1: IDHi-naïve cohorts only
 
	[name], Translational Genomics Research Institute [contact]
9	Pharmacometabolomic Profiling	LC-MS/MS	
 
• Exploratory
 
• To evaluate metabolic signatures
 
	O	(Will be assessed using plasma and bone marrow aspirate collected for 2HG levels.) 
 
• Enrollment, after Cycles 1, 3, 6, 9, 12, and end of treatment
 
	[name], Karmanos Cancer Institute [contact]

\*Availability of bone marrow sample: If a bone marrow procedure is not available for any reason, we can consider using a peripheral blood sample (30 mL per time point) for the different studies, provided that a minimum of 1g/L of circulating blasts are present on the differential of the CBC.

Prioritization of analyses for pauci-cellular samples with low cell yield:

- Metabolomic studies can be done on blood only (DiNardo *et al.*, 2013). We will so prioritize the use of bone marrow for the other exploratory objectives. For bone marrow studies, at enrollment and EOT, the priority will be the WES/RNAseq study followed by single-cell DNA sequencing, avatar studies and the methylation studies. During treatment, the priority will be the WES/RNAseq, single-cell DNA sequencing and the avatar study, which take precedent over the methylation studies.
- The viably cryopreserved bone marrow cells can be used as a back-up for the WES, or themethylation analyses.
- Considering time points: For exploratory objectives, if a prioritization needs to be discussed on serial samples, we will keep as a high priority the baseline, end of Cycle 1, and end-of -treatment (EOT) samples. Samples for end of Cycle 3, 6, 9, and 12 are low priority.

## 5.8 Integral Correlative Study

### 5.8.1 Detection of IDH1/2 Mutations

#### 5.8.1.1 Site Performing Correlative Study

Mutation-detection for eligibility will be conducted by CLIA-certified laboratories. The WES performed by the Molecular Characterization (MoCha) Laboratory (see Section 5.10.1 for details) will be used as a confirmation method, but will not be used for eligibility.

#### 5.9.1.2 Specimen(s) Receipt and Processing

The levels of 2HG in plasma samples will be determined using a validated LC-MS/MS method in Karmanos Cancer Institute (KCI) Pharmacology Core. Samples will be shipped to the KCI Pharmacology Core for analysis. The LC-MS/MS analysis will be performed on an AB Sciex QTRAP 6500 LC-MS/MS system, which consists of an enhanced high-performance hybrid triple quadrupole and linear ion trap mass spectrometer, interfaced with a SHIMADZU Nexera ultra-high-performance liquid chromatography system.

The method has been developed and fully validated for the selectivity, sensitivity, linearity, intra- and inter- accuracy and precision, recovery, and stability, based on the US FDA Guidance to Bioanalytical Method Validation. In brief, the chromatographic separation will be achieved on a Phenomenex Synergi™ Polar-RP column (150 × 2 mm,

4 mcm) using a gradient elution consisting of mobile phase A (0.03% formic acid in water) and mobile phase B (0.03% formic acid in acetonitrile), at the flow rate of 0.25 mL/min. 2HG and its stable isotope-labeled internal standard will be monitored under negative electrospray ionization mode at the mass transitions  $m/z$ ,  $147.0 > 128.9$  and  $150.0 > 131.9$ , respectively.

2HG levels in plasma will be compared to treatment responses. In addition, we will compare 2HG levels with genomic profiling studies proposed below in order to assess whether correlations can be made with (a) co-occurring mutations, (b) gene expression patterns, and (c) methylation profiles.

#### 5.10.1.2 Specimen Receipt and Processing

The levels of 2HG in bone marrow biopsy samples will be determined using a validated LC-MS/MS method in Karmanos Cancer Institute (KCI) Pharmacology Core. Samples will be shipped to the KCI Pharmacology Core for analysis. The LC-MS/MS analysis will be performed on an AB Sciex QTRAP 6500 LC-MS/MS system, which consists of an enhanced high-performance hybrid triple quadrupole and linear ion trap mass spectrometer, interfaced with a SHIMADZU Nexera ultra-high-performance liquid chromatography system.

The method has been developed and fully validated for the selectivity, sensitivity, linearity, intra- and inter- accuracy and precision, recovery, and stability, based on the US FDA Guidance to Bioanalytical Method Validation. In brief, the chromatographic separation will be achieved on a Phenomenex Synergi™ Polar-RP column (150 × 2 mm, 4 mcm) using a gradient elution consisting of mobile phase A (0.03% formic acid in water) and mobile phase B (0.03% formic acid in acetonitrile), at the flow rate of 0.25 mL/min. 2HG and its stable isotope-labeled internal standard will be monitored under negative electrospray ionization mode at the mass transitions  $m/z$ ,  $147.0 > 128.9$  and  $150.0 > 131.9$ , respectively.

2HG levels in bone marrow will be compared to treatment responses. In addition, we will compare 2HG levels with genomic profiling studies proposed below in order to assess whether correlations can be made with (a) co-occurring mutations, (b) gene expression patterns, and (c) methylation profiles.

## 5.10.2 Genomic Profiling (WES, RNAseq, and Infinium Methylation Array)

### 5.10.2.1 Specimen Receipt and Processing at the EET Biobank

Upon receipt at the EET Biobank, the bone marrow and blood will be processed for mononuclear cells using a ficoll-hypaque gradient (baseline and relapse time points) or processed for white blood cells by lysing red blood cells (all other time points). Bone marrow and blood will undergo pathology review to assess the number of blasts. Mononuclear cells and white blood cells will be frozen in a freezing media and stored in a liquid nitrogen vapor phase freezer until distribution for testing. At each time point, DNA and RNA will be co-extracted from bone marrow and blood. Nucleic acids will be stored in a -80°C freezer until distribution for testing.

All samples will be co-extracted for DNA and RNA at each time point.

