### **1.3 Exploratory Objectives**

- 1.3.1 To establish a relationship between treatment response and correlative studies such as plasma and bone marrow 2-Hydroxyglutarate (2HG) levels, and IDH variant allele frequency.
- 1.3.2 To evaluate persistence of double strand breaks in IDH 1/2 mutant AML or MDS.
- 1.3.3 To evaluate response to therapy in the different IDH mutant genotypes.
- 1.3.4 To perform molecular profiling assays on malignant and normal tissues, including, but not limited to, whole exome sequencing (WES), RNA sequencing (RNAseq) order to:
- 1.3.4.1 identify potential predictive and prognostic biomarkers beyond any genomic alteration by which treatment may be assigned.
- 1.3.4.2 identify resistance mechanisms using genomic DNA- and RNA-based assessment platforms.
- 1.3.5 To contribute genetic analysis data from de-identified biospecimens to Genomic Data

Commons (GDC), a well annotated cancer molecular and clinical data repository, for current and future research; specimens will be annotated with key clinical data, including presentation, diagnosis, staging, summary treatment, and if possible, outcome.

- 1.3.6 To bank blood and bone marrow aspirate obtained from patients at the EET Biobank at Nationwide Children's Hospital.

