#### 2.4.3.1 Genomic profiling

Objectives:

- The molecular landscape of *IDH1/2*-mutant AML and MDS predictably determines 2HG level.
- The features on this molecular landscape serve as candidate predictive biomarkers of treatment response.
- To evaluate the impact of olaparib on clonal architecture and clonal evolution.

We hypothesize that 1) the molecular landscape of *IDH1/2*-mutant AML and MDS predictably determines 2HG level, and 2) the features on this molecular landscape serve as candidate predictive biomarkers of treatment response. We will test these hypotheses by comprehensive genomic profiling to elucidate co-occurring mutations, DNA methylation patterns, and gene expression profiles, in all patients enrolled on this study. We will study baseline and on-treatment bone marrow aspirate samples, and also at progression when possible, which also will allow us to assess changes in mutant *IDH1/2* variant allele fractions, and also to probe for the emergence of molecular resistance markers over time.

For the WES studies, we will search for tumor-specific mutations in known oncogenes and tumor suppressors, as well as additional gene mutations. We are particularly interested in mutations known to co-occur with *IDH1/2* mutations: *NPM1*, *FLT3*, *SRSF2*, *DNMT3A*, *NRAS*, *KRAS*, *RUNX1*, *KMT2A*, *PTEN*, *PHF6*, *TP53*, *BCOR*, *STAG2*, etc. (see Figure 10 where 79% of 375 AML cases show genetic alterations from this list). For single cell DNA Seq studies we will base the sequencing panel on mutations identified by the clinical targeted exome and the research WES. We will perform single cell DNA seq on baseline, best response and progression samples. For the RNAseq studies, we will use previously published and publicly available data sets to test whether our cases can be categorized within gene expression clusters found in *IDH1/2*-mutant cancers, using a k-nearest neighbor classification procedure. In addition, we will use RNAseq data to identify recurrent translocations. For the methylation studies, we will use previously published and publicly available data sets (Huang *et al.*, 2018; Benetatos and Vartholomatos, 2018; Wang *et al.*, 2018) to test whether our cases fall within unique methylation clusters found in *IDH1/2*-mutant cancers.

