#### 5.10.5 Evaluation of the clonal heterogeneity evolution by single cell DNA sequencing

##### 5.10.5.1 Specimens will be processed according to institutional SOPs

### 5.10.5.2 Sites performing correlative study

Single cell DNA sequencing will be performed in the laboratories of [name] and [name] at Yale University

We will use patient’s bone marrow samples collected at enrollment and after Cycles 1 [optional], 3, 6, 12 and at end of treatment. Mononuclear cells will be separated using a Ficoll Hypaque purification method and viably cryopreserved in FBS 90%/DMSO10% or other appropriate freezing medium. At time of sequencing batches of 4 samples will be processed at the same time and evaluated using the Mission Bio Tapestri single cell DNA sequencing platform. A minimum of 10^4 living cells are required to proceed for each sample and we will be using the commercially available 45-gene panel. We will compare the evolution of the subclones at the different stages of the treatment, evaluate the proportion of IDH mutated clones persisting after treatment, evaluate the co-mutations as well as the most common mechanisms of resistance (e.g. IDH mutation switch, development of a RAS or FLT3 mutant clone). A subset of the samples (e.g. patients with concomitant IDH and SRSF2 mutations) will be evaluated with a customized panel and another subset of patients will be evaluated using a multi-omic approach using in parallel a barcoded cytometry antibody panel.

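### The biobank's cell preparation switches between baseline and on-treatment samples, so planned changes from baseline in IDH VAF, and in expression and methylation, are confounded with cell fraction (exploratory endpoints only)

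*Combined protocol and SAP*

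**What the plan says.** Section 5.10.2.1 sets the preparation by time point. Marrow and blood arriving at the EET Biobank are "processed for mononuclear cells using a ficoll-hypaque gradient (baseline and relapse time points) or processed for white blood cells by lysing red blood cells", and the lysis route applies to "all other time points". The section continues: "At each time point, DNA and RNA will be co-extracted from bone marrow and blood".

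The biomarker table in Section 5.7 schedules WES as "Mandatory: enrollment, after Cycles 1, 3, 6, 9, and 12", with the Cycle 1 sample limited to IDH-inhibitor-naive cohorts and the end-of-treatment sample optional. RNAseq and methylation use nucleic acid from the same specimens on the same schedule.

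Section 2.4.3.1 intends to use baseline, on-treatment and, where possible, progression marrow to assess change in mutant IDH1/2 "variant allele fractions, and also to probe for the emergence of molecular resistance markers over time". Objective 1.3.1 relates response to correlatives that include 2HG levels "and IDH variant allele frequency".

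For single-cell DNA sequencing, Section 5.7 states "Samples from the biorepository will be used". Section 5.10.5.2 lists marrow from enrollment, Cycles 1 (optional), 3, 6 and 12 and end of treatment, and says: "Mononuclear cells will be separated using a Ficoll Hypaque purification method and viably cryopreserved".

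**The concern.** A density gradient removes most mature granulocytes, whereas red-cell lysis keeps them. Under the written rule a baseline sample is a granulocyte-depleted fraction and an on-treatment sample is not. The switch coincides with the start of olaparib, so a change in VAF between the two may reflect the drug, the laboratory method, or both.

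Expression and methylation profiles depend on cell type. They can therefore shift across the switch even when the mutant clone is equally frequent in all cells. At stake is the interpretation of the exploratory analyses of clonal change under treatment, including any claim that olaparib reduces the IDH-mutant clone.

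**Working it through.** The plan states no figure for this point, so there is none to reproduce. The check is a side-by-side reading followed by an illustrative calculation.

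**1. Which comparisons cross the switch (Sections 5.10.2.1, 5.7, 2.4.3.1)**

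- Baseline to Cycle 1 (IDH-inhibitor-naive only), 3, 6, 9 or 12: Ficoll to lysis. Crosses.
- Baseline to relapse: Ficoll to Ficoll. Does not cross.
- Among Cycles 1, 3, 6, 9 and 12: lysis to lysis. Does not cross.
- Baseline VAF against response: one preparation. Does not cross.

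On-treatment to relapse also crosses, from lysis back to Ficoll.

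**2. Exceptions that mix preparations within a time point**

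Section 5.4.3 has marrow that cannot be shipped on the collection day Ficolled and frozen at the site. The prioritization notes in Section 5.7 allow viably frozen marrow cells as back-up for WES or methylation. Some on-treatment samples may therefore be mononuclear cells. This adds heterogeneity and does not remove the problem.

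**3. Illustrative size for VAF**

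Assumptions, none of them given in the documents: a heterozygous mutation; Ficoll cells free of granulocytes; g = granulocyte share of the lysed white cells; c_m and c_g = mutant-clone fraction in mononuclear cells and in granulocytes; no true change in the marrow.

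- Ficoll: V_F = 0.5 × c_m
- Lysis: V_L = 0.5 × [(1 − g) × c_m + g × c_g]
- Relative change: (V_L − V_F) / V_F = −g × (1 − c_g / c_m)

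Example with c_m = 0.6, c_g = 0 and g = 0.4: V_F = 0.5 × 0.6 = 0.30; V_L = 0.5 × (0.6 × 0.6 + 0.4 × 0) = 0.18; change = (0.18 − 0.30) / 0.30 = −40%.

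| c_m | c_g | V_F | V_L at g = 0.2, 0.4, 0.6 | Apparent change |
|---|---|---|---|---|
| 0.6 | 0 | 0.30 | 0.24, 0.18, 0.12 | −20%, −40%, −60% |
| 0.6 | 0.3 | 0.30 | 0.27, 0.24, 0.21 | −10%, −20%, −30% |
| 0.6 | 0.6 | 0.30 | 0.30, 0.30, 0.30 | 0%, 0%, 0% |
| 0.4 | 0.6 | 0.20 | 0.22, 0.24, 0.26 | +10%, +20%, +30% |

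The largest possible fall equals g. With the same preparation at both time points, the shift due to method is 0 by construction.

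**4. Possible link to response**

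Section 12.1 requires ANC of at least 1.0 × 10^9/L for CR and above 500/mcL for CRh. Neutrophil recovery is thus part of the response definition and may also change g in lysed samples. If so, the error would differ between responders and non-responders and would not average out.

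**5. Whether the plan corrects for it**

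Section 5.10.2.1 records a blast count but states no analytic use for it. Section 9.5 specifies no analysis of VAF, expression or methylation, and no adjustment for preparation or cell composition.

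**6. Single-cell material and end of treatment**

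The table in Section 5.1 sends fresh marrow to Yale only at baseline and end of treatment, so on-treatment single-cell material would come from the biobank. Section 5.10.2.1 assigns lysis to those time points, while Section 5.10.5.2 describes Ficoll mononuclear cells. Separately, Section 5.10.2.1 names a relapse time point but Section 5.1 lists only end of treatment. The preparation for a patient who stops without relapse is not defined.

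**The case against.** The strongest reply is that the exposure is narrow and the endpoints are exploratory. Section 9.5 expects at least 10 samples per time point and technique, for trends only. Section 5.7 ranks the Cycle 3, 6, 9 and 12 samples as low priority when choices must be made. The blast count is a partial covariate, and calling a new mutation present or absent is less sensitive to cell fraction than measuring its level. All of this stands and limits the severity. It does not rescue the baseline to on-treatment contrast, and the same Section 5.7 note gives baseline and end of Cycle 1 high priority.

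Three stronger readings are tempting, and the documents do not support them:

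- A reader might infer that every longitudinal comparison, and objective 1.3.1 as a whole, is compromised. Step 1 shows several comparisons made on like fractions. Objective 1.3.1 does not specify change in VAF, so baseline VAF against response remains usable.
- A reader might infer that VAF falls falsely on treatment and returns at relapse, favoring a positive finding. That requires granulocytes to carry less of the clone. The documents give neither g nor the granulocyte clone fraction, and the sign reverses if granulocytes carry more.
- A reader might infer that the single-cell samples are certainly lysed. Section 5.10.2.1 stands under a heading limited to WES, RNAseq and methylation and does not rule out a separate aliquot, and Section 5.10.5.1 defers to institutional procedures. The sections need reconciling, but loss of the mononuclear material is not established.

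A fair practical objection is that Ficoll may cost cells in marrows that Section 5.7 already expects to be sparse, and that a mid-study switch would itself mix methods.

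**Conclusion.** The concern holds for one planned contrast. Followed as written, the plan confounds baseline to on-treatment change in IDH VAF with cell fraction. The same applies to any such change in expression or methylation, which are measured on the same samples. The conclusion about confounding needs only the processing rule and the fact that the two methods retain different cells.

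The magnitude rests wholly on assumed values: from -60% to +30% over the cases shown, including zero. No single figure should be cited as the expected bias. A link to response is plausible through neutrophil recovery but has not been shown. The primary composite CR, the Simon designs and the plasma 2HG analysis are not touched. Severity is minor.

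**What to change.** 1. In Section 5.10.2.1, use one preparation at every time point for samples not yet processed. Ficoll throughout would also agree with Section 5.10.5.2. Alternatively, keep lysis on treatment and lyse a paired aliquot of each baseline and relapse sample.
2. Record the fraction for every sample, including marrow Ficolled on site and frozen back-up cells.
3. In Section 9.5, limit quantitative longitudinal VAF, RNAseq and methylation comparisons to like fractions, including for samples already processed. Say how the blast count will be used, because matching the preparation does not remove real changes in cell composition.
4. State how end-of-treatment samples without relapse are prepared.
5. Reconcile Sections 5.7, 5.10.2.1 and 5.10.5.2 on the preparation of on-treatment biobank marrow for single-cell sequencing.

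The cost is a change to the biobank work instruction, a fraction field and a few sentences in the analysis plan. No new draw or visit is needed. The downside is lower yield from pauci-cellular on-treatment marrow, eased in part because Section 5.10.2.2 asks for only 100 ng of nucleic acid per assay. A mid-study change would also leave different preparations between patients at the same time point, which the fraction label must handle. For samples already processed, labelling and restricted comparison require no laboratory work.
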